### **3.7.3 withdrawal criteria**

**(1)Patient's miniscrew implantation position develops an infection**

**(2)Patient who produces persistent pain or discomfort that cannot be managed**

**(3)Significant bone resorption around the miniscrew site**

**(4.)The miniscrew becomes loose or shifts position,**

[figure not shown]

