#### **Specific Objective**

The specific objectives for this study will be:

1. To compare the accuracy of miniscrews implanted using modified template by computer-aided design and without template guide (conventional method).

2. To compare the stability of miniscrews implanted using modified template by computer-aided design and without template guide (conventional method).
3. To compare the safety of miniscrews implanted using modified template by computer-aided design and without template guide (conventional method).
4. To compare the accuracy of miniscrew implantation between using CBCT and digital model investigating.

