### **3.5.4 Objective 4**

Sample size calculation based on the objective 1 related to the of guide on the miniscrew implantation. In a previous study the response within each subject group was normally distributed with standard deviation 0.02 um(Talaat S., et al.,2017). If the true difference in the experimental and control means is 0.54, the research will need to study 6 experimental subjects and 6 control subjects to be able to reject the null hypothesis that the population means of the experimental and control groups are equal with probability (power) 0.8. The Type I error probability associated with this test of this null hypothesis is 0.05. The effective size is 1.799001.

Thus, a total sample size for this study will be 24 (12 for experimental and control group) after considering 20% drop-out.

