**(5)Patient who is allergic to the material of the miniscrew**

Reference population: Orthodontic patient Chinese ethnic group

Source population: Orthodontic patient in Beijing TCM hospital

Inclusion criteria and exclusion criteria

Patients randomly divided into 2 groups with randomization

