## 3.10 Data collection and grouping

Twenty four (24) individuals who met the criteria will be randomly divided into 2 groups, 12 will be selected as the experimental group and mini-implants will be

implanted using guide plates, while others 12 participants will be selected as the control group and implanted mini-implants based on experience and no guide plates.

**The recruitment will take about two months, using hospital bulletin boards and social media at Beijing Xuanwu TCM Hospital. All routine orthodontic diagnostic records will be collected. The patient was asked to sign an informed consent form before surgery, which took about 20 to 30 minutes. The doctor implanted the miniscrew, and the operation time was about half an hour. The study design will be used as assigning intervention and control group randomly. The postoperative clinical and imaging evaluation was about 6 months.**

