### 3.13 Analyses and measurements:

#### 1. Main efficacy indicators.

A. CBCT analysis indicators: Based on the ideal position of the implant designed before surgery as the standard, the researcher will measure the linear deviation of the tip and cap of the TADs in the mesio-distal, buccal-lingual, and vertical three-dimensional directions, the angle deviation of the tip and cap of the TADs in the mesio-distal, buccal-lingual, and vertical three-dimensional directions, the distance between TADs and tooth root and maxillary sinus, and the distance between two tooth roots.

B. Clinical data analysis: The mobility of TADs. : The stability of a miniscrew can be evaluated through clinical examination by checking for mobility, and implant loosening and displacement.

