**-the distance between TADs and tooth root and maxillary sinus, and the distance between two tooth roots.**

**-the thickness of cortical bone and cancellous bone**

**4.Stability of miniscrews : -Looseness of mini-implant**

**5.Safety of miniscrews : Distant of the root to the miniscrew tip**

**Distant between miniscrew tip to the maxillary sinus**

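### Section 3.7.3 withdraws patients when the miniscrew loosens or shifts, which is the trial's own stability outcome

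*Protocol*

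**What the plan says.** Section 3.7.3 of the protocol gives five withdrawal criteria. Criterion (4) is "The miniscrew becomes loose or shifts position". Criterion (1) is infection at the implant position, criterion (3) is "Significant bone resorption around the miniscrew site", criterion (2) is pain or discomfort that cannot be managed, and criterion (5) is "Patient who is allergic to the material of the miniscrew".

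The outcomes are set elsewhere in the same document:

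- Objective 2 (section 1.11.2) is "To compare the stability of miniscrews implanted using modified template" against the conventional method.
- Section 3.13, under the main efficacy indicators, says "The stability of a miniscrew can be evaluated through clinical examination by checking for mobility, and implant loosening and displacement". Item 4 of that section lists stability as "Looseness of mini-implant".
- Section 3.9.2.1 names looseness and shedding rate as dependent variables.
- Section 3.13 lists signs of bone loss or inflammation around the screw among the secondary indicators. Section 3.18 names infection at the site, and a loose or dislodged screw, as complications.

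On follow-up, section 3.10 states "The postoperative clinical and imaging evaluation was about 6 months", and section 3.11 places T1 immediately after insertion and T2 at 6 months. Section 3.5.4 sets the total at 24, 12 per arm, "after considering 20% drop-out". No section says that a patient withdrawn for loosening counts as a failure, stays in follow-up or stays in the analysis.

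**The concern.** A withdrawal rule should not be triggered by the event the trial sets out to count. Here criterion (4) and the stability outcome are the same event, and criteria (1) and (3) overlap with the inflammation, bone-loss and complication outcomes. Three of the five criteria therefore remove patients because an outcome has occurred.

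Two things are at stake. First, later follow-up for root resorption, bone and complications stops in the patients in whom it matters most. Second, a screw failure carries the same label as an ordinary drop-out. If it is handled as one, the failure rates in both arms are understated, and the arm with more failures is flattered more.

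**Working it through.** **Step 1. Outcome and withdrawal rule side by side**

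| Event | Role as outcome | Role in 3.7.3 |
|---|---|---|
| Loosening or displacement | Stability, objective 2 (3.13; looseness also in 3.9.2.1) | Criterion (4) |
| Bone loss around the screw | Secondary CBCT indicator (3.13) | Criterion (3) |
| Infection | Named complication (3.18); inflammation is a CBCT indicator (3.13) | Criterion (1) |

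The first row is a direct match, the second close, the third indirect.

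**Step 2. The plan's own drop-out allowance**

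The largest stated requirement before drop-out is 10 per arm (3.5.3). With its stated effect size of 1.3929508, two-sided alpha 0.05 (sidedness assumed) and power 0.80, a two-sample t-test needs 9.16, so 10 per arm. Then 10 × (1 + 0.20) = 12 per arm, or 24 in total, which reproduces the stated figure. The allowance is 12 − 10 = 2 patients per arm.

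**Step 3. How many patients criterion (4) might remove**

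The protocol gives no loosening rate per arm. Section 3.5.2 quotes 86% success and 2% failure without assigning either to an arm. The rates below are assumptions: guided 2% throughout, control 5% to 20%, with 14% being the complement of 86%.

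- Expected events = 12 × control rate + 12 × guided rate. At 14%: 1.68 + 0.24 = 1.92 of 24, or 8.0%.
- Share of the control arm's allowance at 14%: 1.68 / 2 = 84%.
- Chance of exceeding the allowance = P(3 or more of 12), binomial with the control rate.
- Power = two-sided Fisher exact test at 0.05, 12 per arm, every failure counted.

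| Control rate | Expected events of 24 | P(3 or more in control) | Fisher power |
|---|---|---|---|
| 5% | 0.84 | 2% | 0.01% |
| 10% | 1.44 | 11% | 0.3% |
| 14% | 1.92 | 23% | 1.4% |
| 20% | 2.64 | 44% | 5.8% |

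**Step 4. What misclassification would do**

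If every loosened screw leaves as a drop-out and the remainder are compared, the numerator is zero in each arm by construction, so assumed rates of 14% and 2% would be reported as 0% and 0%. An extreme example: with 0/12 guided and 6/12 control failures, Fisher's test gives p = 0.014. With the six booked as drop-outs, the comparison is 0/12 against 0/6, with no events and nothing to detect.

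**Step 5. What is not affected**

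Accuracy at T1 is measured immediately after insertion, before any later loosening.

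**The case against.** Five points can be made for the plan.

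- **Loosening will be recorded.** It must be seen to trigger withdrawal, and Annexure C is a monthly stability grid by group. This stands: if the event is scored as a failure when found, little is lost for a yes/no outcome. But the grid sets no scoring rule and does not keep the patient in the study.
- **The 0% against 0% result needs an analysis the protocol does not prescribe, and its handling could sit in a statistical analysis plan.** This stands as a limit on the claim, and that result is only a possibility. An analysis plan cannot, however, recover data that were never collected because the protocol withdrew the patient.
- **Withdrawal might mean only stopping the device.** The term is undefined, but leaving the study is its ordinary meaning, and no text limits it to the device. Section 3.18 commits the hospital to paying for treatment of complications, which is care and not research follow-up. It is true that T2 position cannot be measured on a lost screw under any wording.
- **The allowance of 2 per arm is borrowed from objective 3.** Section 3.5.2 asks for only 8 per arm for stability, leaving 12 − 8 = 4 spare. On that basis the chance of exceeding the allowance (5 or more of 12) is 0.02%, 0.4%, 1.8% and 7.3% at control rates of 5%, 10%, 14% and 20%. The arithmetic is right, but the trial has one allowance, built by going from 10 to 12. What stands is that overrunning it does not by itself show lost power: distances taken from post-insertion imaging survive later loosening.
- **No informative test is damaged.** This also stands. Fisher power is at most 5.8% over the assumed range, so the harm is to descriptive rates and to follow-up.

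**Conclusion.** The concern holds. Criterion (4) makes the stability outcome a reason to leave the study, and criteria (1) and (3) do much the same for infection and bone loss. On the ordinary meaning of withdrawal, follow-up before T2 is lost in exactly these patients. The distortion of the stability comparison is conditional on failures being counted as drop-outs. Under the assumed rates, between 0.84 and 2.64 of 24 patients would be expected to meet criterion (4), and the chance of overrunning the control arm's two spare patients runs from 2% to 44%. These figures illustrate scale only; the conclusion comes from the conflict between sections 3.7.3 and 3.13 and depends on none of them. It should be fixed before recruitment.

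**What to change.** In section 3.7.3, separate stopping the device from leaving the study:

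- Reword criteria (1), (3) and (4) as outcome events that may lead to screw removal at clinical judgement but do not end participation.
- Keep criteria (2) and (5) as grounds for stopping the device, with outcome follow-up continuing where the patient consents.
- Keep every such patient in follow-up to 6 months and in the analysis by randomised group.
- State that screw failures do not count against the 20% drop-out allowance.

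In section 3.13, add one sentence to the stability definition: any loosening, displacement or shedding is a stability failure at the date it is found. Report T2 position as conditional on the screw being retained.

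The cost is a change of wording and continued follow-up of a few patients whose screw has failed. The sample size does not change.

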**(5)Patient who is allergic to the material of the miniscrew**

Reference population: Orthodontic patient Chinese ethnic group

Source population: Orthodontic patient in Beijing TCM hospital

Inclusion criteria and exclusion criteria

Patients randomly divided into 2 groups with randomization

### 3.9 Variables and tools

#### 3.9.1 Research tool

3.9.1.1 Routine orthodontics records before treatment

History and examination record

Digital model

CBCT

### 3.9.1.2 Routine orthodontics records after treatment

Digital model

Dental record models

CBCT

### 3.9.1.3 Special need to conduct the research

Ordinary gypsum (Hubei Jingmen Shishengtang Gypsum Industry .)

Dental alginate impression material (Beijing Hongye Dental Medical Equipment Factory)

Micro implant nail (Ningbo Cibei Medical Equipment )

Screwdriver (Ningbo Cibei Medical Equipment .)

Guide plate resin material (Beijing Xikema Medical Equipment)

3D Metal Materials (Beijing Xikema Medical Equipment )

CBCT (5G, version FP; NewTom, Verona, Italy)

Software Segma Guide (Beijing Xikema Medical Equipment )

D700 scanner (3Shape, Denmark)

Itero scanner(invisalign,American)

3D printer (Beijing Xikema Medical Equipment)

### **3.9.2 Variables**

#### **3.9.2.1 Dependent variables**

Clinical variables

-Looseness of mini-implant

-Shedding rate of mini-implant

-depth of exploration,

-gingival type

-gingival color and texture

-plaque index

-bleeding index

#### **3.9.2.2 Variables for digital dental models acquisition**

Distant of the root to the miniscrew tip

Distant between miniscrew tip to the maxillary sinus

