#### **1.4 Cone-Beam computed tomography (CBCT)**

Cone-beam computed tomography (CBCT) has been introduced for dental offices because of the reduced costs and size (Patel et al., 2009a; Patel et al., 2009b). The scans produced by a CBCT imaging system have a significantly reduced scan time, reduced cost for the patient, and use a lower radiation dose than medical CT (Ziegler et al., 2002; Scarfe et al., 2006). Different CBCT machines will have different radiation doses determined by the particular brand, settings, and the area of the mouth to be scanned. CBCT compensates for the disadvantage of the scanning method, which is that only the crown can be scanned. It also provides significant dose reductions of between 98.5% and 76.2% when compared to the patient dose reported for maxillofacial imaging by conventional CT (approximately 2000 mSv) (Scarfe WC,et al., 2008; Loubele M et al., 2009). Initial research on the accuracy of CBCT focused on the evaluation of linear (Goodarzi ,et al., 2015; Sherrard JF et al., 2010)or volumetric data, (Wang Y ,et al., 2011; Tayman MA et al., 2019) and was shown to be highly accurate with regard to alveolar bone defects and root length of varying voxel sizes (0.125–0.40 mm) (Damstra J ,et al., 2010; Lyu H et al., 2023).

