**5) The process of implanting implant nails on the Control Group is as follows:**

**Similar to the intervention group, but the doctor implant the miniscrew based on experience with CBCT scans.**

6) Collect date before and after implant nail implantation. The digital plaster models will be obtained by scanning with a D700 scanner (3shape, Denmark). Both digital models and CBCT scan data will be imported into Segma implant guide software (Beijing, China). The combination method is as follows: first, open the file in a way that only uses CBCT for implant design and adjust the density of anatomical landmarks such as the maxillary sinus, condylar foramen, or protrusions to an explicit level. Then, the teeth or jaw landmark points of the model and CBCT will be selected to reconstruct a 3D model.

4) The data collection will be performed by obtaining plaster model using intraoral scanner at T1(immediate post insertion) and T2 (6 months post insertion)

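### Objective 4 (CBCT versus digital model) is not validly set up: the digital-model variables need CBCT data, and a within-participant comparison is sized as two independent groups

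*Protocol*

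**What the plan says.** The fourth specific objective (Protocol 1.11.2) is "To compare the accuracy of miniscrew implantation between using CBCT and digital model investigating". This compares two measuring methods, not two treatments.

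Section 3.9.2.2 lists two variables for the digital model: "Distant of the root to the miniscrew tip" and "Distant between miniscrew tip to the maxillary sinus". Section 1.4 states that "CBCT compensates for the disadvantage of the scanning method, which is that only the crown can be scanned".

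Sections 3.9.2.3 and 3.13 (item 1A) assign the linear and angular deviations from the planned position to CBCT. They also give CBCT the distances from the screw to root and sinus.

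Section 3.11, item 6, has model and CBCT data imported into one software package: "Then, the teeth or jaw landmark points of the model and CBCT will be selected to reconstruct a 3D model". On the source of the model, item 6 says "The digital plaster models will be obtained by scanning with a D700 scanner", while the last item of the section speaks of "obtaining plaster model using intraoral scanner at T1(immediate post insertion) and T2 (6 months post insertion").

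Sections 3.9.1.1 and 3.9.1.2 list both digital model and CBCT among the routine records before and after treatment. Section 3.5.4 nevertheless concludes that "the research will need to study 6 experimental subjects and 6 control subjects", with power 0.8, type I error 0.05, SD 0.02 um, difference 0.54 (no unit) and effect size 1.799001. The tests named in 3.14 are Kruskal-Wallis across three groups, Bonferroni-corrected pairwise comparisons and one-way ANOVA.

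**The concern.** A comparison of two measuring methods needs the same quantity, obtained by each method without help from the other, on the same objects. Objective 4 does not secure this. The quantities listed for the digital model are ones the protocol's own description of scanning says it cannot see. The deviation quantities, to which a post-insertion scan could contribute through the screw head, are not assigned to it. The sample size and the tests treat the two methods as if they were applied to different people.

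At stake is what the objective can report. If the digital-model value borrows its anatomy from CBCT, agreement between the methods is partly a product of the workflow. A palatal study summarised in Table 2.2 found that oral scans and CBCT after surgery gave differing accuracy results; shared data could hide a difference of that kind. Independent-samples tests on paired readings would also give a wrong standard error for the difference.

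**Working it through.** **1. What each method can supply**

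| Quantity | Listed for digital model (3.9.2.2) | Listed for CBCT (3.9.2.3, 3.13) | Visible on a crown-only scan (1.4) |
|---|---|---|---|
| Root to screw tip | yes | yes, as screw-to-root distance | no |
| Screw tip to sinus | yes | yes, as screw-to-sinus distance | no |
| Linear deviation from plan, cap and tip | no | yes | cap only, assuming the exposed head is captured |
| Angular deviation from plan | no | yes | axis only, from the exposed head |

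The methods overlap only in the first two rows, which the scan cannot measure alone. No accuracy variable is both shared and measurable by the scan in its own right.

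**2. Dependence under each reading of 3.11, item 6**

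- Postoperative CBCT merged: tip, root and sinus all come from the comparator. Dependence is complete.
- Preoperative CBCT merged: the screw head could come from the scan independently, but root and sinus still come from CBCT. Dependence is partial.

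Item 6 does not say which applies or how the tip is located.

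**3. Reproducing the stated 6 per group**

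Inputs from 3.5.4: d = 1.799001, power 0.80, alpha 0.05 (sidedness not stated; two-sided assumed). Independent two-sample t-test, noncentral t:

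- n = 5 per group: power 0.7033
- n = 6 per group: power 0.8015

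The figure reproduces as a two-independent-groups calculation. The normal approximation, 2(1.960 + 0.842)²/1.799² = 4.85, gives 5, and so does a one-sided t-test (power 0.828).

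**4. Internal consistency of 3.5.4**

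- Stated difference / stated SD = 0.54 / 0.02 = 27, not 1.799. At 27, 1 per group (normal approximation) or 2 (t-test) would do.
- SD implied by the stated effect size = 0.54 / 1.799001 = 0.30.

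The difference, SD and effect size cannot all be right.

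**5. The same effect size in a paired design**

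The standardised paired difference is dz = d / √(2(1 − ρ)). The protocol gives no within-pair correlation ρ, so a range is assumed. One-sample t-test on the differences, two-sided 0.05, power at least 0.80:

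| ρ (assumed) | dz | Pairs | Power |
|---|---|---|---|
| 0 | 1.272 | 8 | 0.868 |
| 0.3 | 1.520 | 6 | 0.842 |
| 0.5 | 1.799 | 5 | 0.847 |
| 0.7 | 2.323 | 4 | 0.858 |
| 0.9 | 4.023 | 3 | 0.911 |

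If 1.799 is itself the standardised paired difference, 5 pairs suffice. The plan has 24 participants, or 24 × 0.8 = 19.2, so about 19, after the allowed 20% drop-out. A sample size for agreement cannot be computed, because the protocol gives neither an acceptable limit nor an SD of differences.

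**The case against.** The strongest reply is that 2.3.2 describes an integrated model built from CBCT and intraoral scan data. If that is what the digital model means, the root and sinus distances do exist. This stands: one cannot say the digital-model value is impossible to obtain. What remains is that it is not independent of CBCT.

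A reader might go further and infer that the comparison is fully circular, with the two methods bound to agree. The text does not support that. In 3.11, item 6, the before-and-after wording governs data collection, and the merging steps begin with opening a file for implant design, which reads as planning. A post-insertion scan could also capture the screw head independently.

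A reader might also link the two screw lengths (10 mm in 3.11, 13 mm in 3.12) to a 3 mm error in a tip position projected from the head. The protocol never describes such a projection, and 3.13 lists implant length among the recorded clinical indicators. The two lengths contradict each other and must be reconciled, but as a separate matter.

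The two distances reappear in 3.13 under safety, so they may have been meant for objective 3. Section 3.13, item 3, also counts the screw-to-root and screw-to-sinus distances as accuracy, so the overlap with objective 4 is real. If the distances belonged to safety only, objective 4 would have no digital-model variable at all.

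Naming both scanners need not be an error, since 3.9.1.3 lists both and they may serve different steps. The fault is only that 3.11 leaves unclear which one produces the post-insertion model.

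Finally, an agreement analysis could be left to a statistical analysis plan. But 3.5.4 fixes a two-group structure for objective 4, and every test that 3.14 names is for independent samples.

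**Conclusion.** The point holds. As written, objective 4 would not give a valid comparison of the two methods. The listed digital-model variables cannot be measured without CBCT, the accuracy deviations are assigned to CBCT alone, and the sizing and stated tests are for separate groups although both methods are recorded on the same participants. Dependence on the comparator is at least partial, and complete only if the postoperative CBCT is the one merged.

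The wrong sizing structure might be read as leaving the trial too small. It does not: 3 to 8 pairs are enough over assumed correlations of 0.9 to 0. That statement rests on the effect size of 1.799, which conflicts with the stated difference and SD (ratio 27; implied SD about 0.30), so its basis needs restating. The conclusion also assumes two-sided testing and that 1.4 correctly describes what the scan shows. The change should be made before data are collected; it bears on objective 4 and not on the comparison of guide with no guide.

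**What to change.** - **3.9.2.2:** define the digital-model measurement as cap position and long-axis angle from the post-insertion scan, registered on tooth crowns to the preoperative CBCT only. Move the root and sinus distances to the CBCT list.
- **3.11:** state which CBCT is merged for which purpose, and which scanner produces the post-insertion model.
- **Comparator:** the same quantities from a postoperative CBCT taken at the same visit as the scan. Section 3.9.1.2 gives that CBCT no date and 3.10 says only that postoperative evaluation takes about 6 months. If none is planned at T1, use the T2 scan, so that screw movement is not mixed with method difference.
- **3.14:** analyse paired differences (mean difference with limits of agreement). Annexure A has right- and left-side columns, so allow for more than one screw per patient if both sides are used.
- **3.5.4:** restate as a paired calculation with a difference, SD and effect size that agree and carry units.
- **Separately:** reconcile the 10 mm and 13 mm screw lengths in 3.11 and 3.12.

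The cost is wording in four sections. No added enrolment is needed at the stated effect size, and the scans are already among the listed records, provided a CBCT and a scan fall at the same visit. The downsides are that root and sinus clearance can no longer be claimed from the scan alone and that, if T2 is used, the comparison covers only screws still in place at 6 months.
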